7.3 Subject Population(s) for Analysis

All subjects who completed the study protocol will be included in the study analysis.

8 Safety and Adverse Events

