4.3 Subject Recruitment and Screening

Patients will be recruited through the routine work of the Dermatology departments at the Hospital of the University of Pennsylvania. Recruitment and consent will be obtained by the principle investigator or another Dermatology physician as delegated by the investigator seeing the patient in the outpatient clinic. Patients seen in the outpatient clinic with clinical representation of keloids will be approached by the

CONFIDENTIAL

Dermatology attending as part of clinical evaluation, and written, informed consent will be obtained from the patient prior to any research related procedures are conducted.

It will be explained to the potential participant that entry into the trial is entirely voluntary and that their treatment and care will not be affected by their decision. Should any Penn affiliates be approached, that their decision of whether to participate will not impact their standing with the institution. It will also be explained that they can withdraw at any time. In the event of their withdrawal it will be explained that their data collected so far will be retained and used as part of the study analysis.

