4.4 Early Withdrawal of Subjects

4.4.1 When and How to Withdraw Subjects

The participant will stop Imiquimod treatment early for the following reasons:

- New clinical/diagnostic information (e.g. pathology report) suggests a diagnosis other than keloid
- Intolerable local or systemic toxicity from Imiquimod
- Clinical evidence of keloid recurrence. These participants will progress to intralesional steroid injections or excision as per standard of care.
- Any participant who becomes pregnant during the study
- Withdrawal of consent

Subjects who withdraw consent will be withdrawn from the trial. The subjects will be made aware that this will not affect their standard of care. Subjects will be made aware (via the information sheet and consent form) that should they withdraw the data collected will be retained and used as part of the study analysis.

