4.4.2 Data Collection and Follow-up for Withdrawn Subjects

Protected Health Information to be collected include names and medical record numbers. Additional information that is to be collected from patient's electronic medical record are:

- Race/ethnicity/gender
- And all elements of dates for dates that are directly related to the patient
- Current medications
- Symptoms related to treatment
- Physical examination
- Treatment and response
- Unidentifiable photodocumentation of lesions

Patients who choose to withdraw from the trial will be asked for permission for phone follow-up 12 weeks after excision date.

Patients who are withdrawn from the study for any reason but have initiated at least 1 imiquimod treatment will be seen in the outpatient clinic for one additional follow-up visit after their withdrawal date to observe the application site.

This information will be associated with a study ID. A master list with PHI and study IDs will be maintained by personal investigators in a secure location. Access will be given to only study personnel as needed. Data sets will only include assigned study IDs. Data will be backed up as a password protected file on a Penn Medicine secure server. Links to identifiers will be destroyed after the study is completed.

5 Study Drug

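### Section 7.3 names one analysis population, undefined protocol completers, with no rule for withdrawals, and is not reconciled with the statements that withdrawn subjects' data will be used

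*Combined protocol and SAP*

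**What the plan says.** Section 7.3 is a single sentence: "All subjects who completed the study protocol will be included in the study analysis". No other analysis set appears, for efficacy or for safety. Section 7.2 reports a response rate as a percentage with a 95% confidence interval and has no rule for missing outcomes.

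On withdrawal, Section 4.3 says subjects will be told that "their data collected so far will be retained and used as part of the study analysis", and Section 6 repeats this. Section 4.4.1 says the information sheet and consent form will state that "should they withdraw the data collected will be retained and used as part of the study analysis".

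Section 4.4.1 also opens a list with "The participant will stop Imiquimod treatment early for the following reasons". The list includes "Clinical evidence of keloid recurrence. These participants will progress to intralesional steroid injections or excision as per standard of care" and "Intolerable local or systemic toxicity from Imiquimod". The section then adds: "Subjects who withdraw consent will be withdrawn from the trial". Section 4.4.2 provides one further clinic visit for "Patients who are withdrawn from the study for any reason but have initiated at least 1 imiquimod treatment", and asks those who choose to withdraw for permission to telephone at 12 weeks after excision.

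Section 7.1 assumes 70% recurrence at 8 weeks after excision alone and 25% with imiquimod. It requires 8 subjects and enrols 10 to allow for about 20% withdrawal.

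**The concern.** The trial reports one efficacy figure, and its denominator is not fixed. A subject whose recurrence is seen at week 2 or 4 and who then withdraws has a known primary outcome. Under a completers-only reading of Section 7.3 that outcome is lost. Under Sections 4.3, 4.4.1 and 6 it is used. Nothing says which governs the rate.

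The term itself is also open. Completion could mean finishing the 6-week course (Section 5.2), attending the visit 8 weeks after excision (study week 10), or answering the call 12 weeks after excision (study week 14). Eligibility asks for 10 weeks of availability (Section 4.2), while participation is about 14 weeks (Section 3.1). A subject who attends every clinic visit but misses the call cannot be classified.

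With 10 subjects in an open-label study, where the investigator judges recurrence in clinic, one or two classification decisions can move the reported rate appreciably. As written, those decisions could be made after the outcomes are known.

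**Working it through.** **Inputs.** Historical recurrence p0 = 0.70, expected recurrence p1 = 0.25, 80% power, alpha 5%, 8 subjects needed, about 20% withdrawal, 10 enrolled (all Section 7.1). Percentage with 95% CI (Section 7.2).

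**Step 1: reproduce the plan's figure.** One-sample normal approximation, two-sided 5%:

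n = [(1.960 × √(0.70 × 0.30) + 0.842 × √(0.25 × 0.75)) / (0.70 − 0.25)]² = 7.87, so 8.

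Inflation for withdrawal: 8 / (1 − 0.20) = 10.

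Both figures reproduce, although the plan does not state the test or its sidedness. Inflating for withdrawal makes sense if withdrawn subjects do not contribute to the rate, so Section 7.1 points towards a completers-only analysis.

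**Step 2: what two subjects can do.** With 25% recurrence among 8 completers, the result is 2/8. The outcomes of the two withdrawn subjects are an assumption, so all three possibilities are shown. Intervals are exact (Clopper-Pearson): the lower limit is the 0.025 quantile of Beta(x, n − x + 1) and the upper limit is the 0.975 quantile of Beta(x + 1, n − x).

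| Analysis | Rate | 95% CI | Includes 70%? |
|---|---|---|---|
| Completers, 2/8 | 25% | 3.2-65.1% | No |
| Neither withdrawn subject recurred, 2/10 | 20% | 2.5-55.6% | No |
| One recurred, 3/10 | 30% | 6.7-65.2% | No |
| Both recurred, 4/10 | 40% | 12.2-73.8% | Yes |

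If withdrawal were unrelated to outcome at the plan's 25%, both recurring would have probability 0.25² = 6.25%. It becomes more likely if withdrawal is linked to recurrence, and the documents give no figure for that link.

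**Step 3: direction.** Let f be the share of recurrers left out of the rate. The documents give no value, so the full range is shown. The expected reported rate is p(1 − f) / (1 − pf).

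| f | True 25% | True 70% |
|---|---|---|
| 0 | 25.0% | 70.0% |
| 0.25 | 20.0% | 63.6% |
| 0.50 | 14.3% | 53.8% |
| 0.75 | 7.7% | 36.8% |
| 1 | 0% | 0% |

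Losing non-recurrers acts the other way. If a share g = 0.20 of them is left out (assumed), the rate is p / [p + (1 − p)(1 − g)]: 0.25 / 0.85 = 29.4% and 0.70 / 0.94 = 74.5%. Equal shares cancel: with f = g = 0.20, 0.20 / (0.20 + 0.60) = 25%. The sign of the bias therefore depends on who is left out, which Section 7.3 does not settle.

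**The case against.** The strongest reply is that the passages can all be true together. Section 7.3 says completers are included and does not say that others are not. Sections 4.3, 4.4.1 and 6 describe what participants are told about their data, not how a rate is built. This stands to the extent that a flat contradiction, which a reader might infer, is not established. What remains is that no passage reconciles them, no second set exists, and the 8-of-10 allowance fits completers only.

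A reader might also infer that the plan drops patients because they recurred, since recurrence is listed under the early-withdrawal heading. The documents do not support that as the plan's meaning. The list gives reasons for stopping the drug, and only withdrawal of consent is expressly withdrawal from the trial. The Section 6 schedule carries recurrence checks through to the phone call, with no exception for subjects off drug. A recurrer managed as Sections 4.4.1 and 6.4 describe has arguably followed the protocol. The reading stays possible, because completion could mean completing the drug course and Section 4.4.2 speaks of withdrawal for any reason, but it is the weaker one.

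A third inference is that subjects stopping for toxicity would vanish from the tolerability result. No passage says so. Sections 4.4.2, 6.4 and 8.2 already require an extra visit, an unscheduled visit and recording of all adverse events. The gap is only that no safety set is named.

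Finally, this is a small descriptive pilot, and in two of the three cases in Step 2 the interval still excludes 70%. That is correct and limits the severity.

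**Conclusion.** The concern holds in a limited form. The only stated population rests on an undefined term, no rule covers withdrawals, and three statements on the use of withdrawn subjects' data are not reconciled with it. Outcomes already observed could be left out of the one efficacy figure.

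On the plan's own counts, the choice moves the rate from 25% to between 20% and 40%. Only the extreme case, with both withdrawn subjects recurring, brings the 70% historical rate inside the interval. This assumes exactly two withdrawals and 2/8 among completers. The calculations with f and g illustrate direction and do not estimate bias. Section 7.2 has no success threshold, so what changes is how the result reads against 70%, not a formal test. This should be fixed before outcomes are examined. It does not invalidate the design, and the 8 and 10 in Section 7.1 are unaffected.

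**What to change.** Replace Section 7.3 with two defined sets and a counting rule:

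- **Efficacy set:** all subjects who applied at least one dose and had the keloid excised, excluding only those whose pathology shows another diagnosis.
- **Primary time point:** the visit 8 weeks after excision, on which Section 7.1 is based.
- **Counting rule:** any recurrence observed up to that visit counts as recurrence, whether or not imiquimod was stopped and whatever treatment followed.
- **Missing outcomes:** report the number of subjects with no outcome, and the rate with all of them counted as recurrence and with all counted as no recurrence. On the Step 2 figures, with both withdrawn subjects' outcomes unknown, that is 4/10 and 2/10.
- **Completers:** a sensitivity analysis only, with completion defined, including whether the 12-week call is required.
- **Safety and tolerability set:** all subjects with at least one application, using data already collected under Sections 4.4.2, 6.4 and 8.2.

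Reconcile the new text with Sections 4.3, 4.4.1 and 6, so that what subjects are told matches the analysis.

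The cost is a few sentences and a reported rate that may change slightly in either direction. Some outcomes after withdrawal will stay unknown, because the 12-week call needs the subject's permission. The two bounds show how much that matters. No visit, dose or clinical rule changes.

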8.1 Definitions

Unanticipated Problems Involving Risk to Subjects or Others

Any incident, experience, or outcome that meets all of the following criteria:

- Unexpected in nature, severity, or frequency (i.e. not described in study-related documents such as the IRB-approved protocol or consent form, the investigators brochure, etc)
- Related or possibly related to participation in the research (i.e. possibly related means there is a reasonable possibility that the incident experience, or outcome may have been caused by the procedures involved in the research)
- Suggests that the research places subjects or others at greater risk of harm (including physical, psychological, economic, or social harm).

Adverse Event

An **adverse event** (AE) is any symptom, sign, illness or experience that develops or worsens in severity during the course of the study. Intercurrent illnesses or injuries should be regarded as adverse events. Abnormal results of diagnostic procedures are considered to be adverse events if the abnormality:

- results in study withdrawal
- is associated with a serious adverse event
- is associated with clinical signs or symptoms
- leads to additional treatment or to further diagnostic tests
- is considered by the investigator to be of clinical significance

Serious Adverse Event

Adverse events are classified as serious or non-serious. A **serious adverse event** is any AE that is:

- fatal
- life-threatening
- requires or prolongs hospital stay
- results in persistent or significant disability or incapacity
- a congenital anomaly or birth defect
- an important medical event

CONFIDENTIAL

Important medical events are those that may not be immediately life threatening, but are clearly of major clinical significance. They may jeopardize the subject, and may require intervention to prevent one of the other serious outcomes noted above. For example, drug overdose or abuse, a seizure that did not result in in-patient hospitalization, or intensive treatment of bronchospasm in an emergency department would typically be considered serious.

All adverse events that do not meet any of the criteria for serious should be regarded as **non-serious adverse events**.

Adverse Event Reporting Period

The study period during which adverse events must be reported is normally defined as the period from the initiation of any study procedures to the end of the study treatment follow-up. For this study, the study treatment follow-up is defined as 30 days following the last administration of study treatment.

Preexisting Condition

A preexisting condition is one that is present at the start of the study. A preexisting condition should be recorded as an adverse event if the frequency, intensity, or the character of the condition worsens during the study period.

General Physical Examination Findings

At screening, any clinically significant abnormality should be recorded as a preexisting condition. At the end of the study, any new clinically significant findings/abnormalities that meet the definition of an adverse event must also be recorded and documented as an adverse event.

Post-study Adverse Event

All unresolved adverse events should be followed by the investigator until the events are resolved, the subject is lost to follow-up, or the adverse event is otherwise explained. At the last scheduled visit, the investigator should instruct each subject to report any subsequent event(s) that the subject, or the subject's personal physician, believes might reasonably be related to participation in this study. The investigator should notify the study sponsor of any death or adverse event occurring at any time after a subject has discontinued or terminated study participation that may reasonably be related to this study. The sponsor should also be notified if the investigator should become aware of the development of cancer or of a congenital anomaly in a subsequently conceived offspring of a subject that has participated in this study.

Abnormal Laboratory Values

A clinical laboratory abnormality should be documented as an adverse event if any one of the following conditions is met:

- The laboratory abnormality is not otherwise refuted by a repeat test to confirm the abnormality
- The abnormality suggests a disease and/or organ toxicity
- The abnormality is of a degree that requires active management; e.g. change of dose, discontinuation of the drug, more frequent follow-up assessments, further diagnostic investigation, etc.

Hospitalization, Prolonged Hospitalization or Surgery

Any adverse event that results in hospitalization or prolonged hospitalization should be documented and reported as a serious adverse event unless specifically instructed otherwise in this protocol. Any condition responsible for surgery should be documented as an adverse event if the condition meets the criteria for and adverse event.

Neither the condition, hospitalization, prolonged hospitalization, nor surgery are reported as an adverse event in the following circumstances:

- Hospitalization or prolonged hospitalization for diagnostic or elective surgical procedures for a preexisting condition. Surgery should **not** be reported as an outcome of an adverse event if the purpose of the surgery was elective or diagnostic and the outcome was uneventful.
- Hospitalization or prolonged hospitalization required to allow efficacy measurement for the study.

CONFIDENTIAL

- Hospitalization or prolonged hospitalization for therapy of the target disease of the study, unless it is a worsening or increase in frequency of hospital admissions as judged by the clinical investigator.

8.2 Recording of Adverse Events

At each contact with the subject, the investigator must seek information on adverse events by specific questioning and, as appropriate, by examination. Information on all adverse events should be recorded immediately in the source document, and also in the appropriate adverse event module of the case report form (CRF). All clearly related signs, symptoms, and abnormal diagnostic procedures results should be recorded in the source document, though should be grouped under one diagnosis.

All adverse events occurring during the study period must be recorded. The clinical course of each event should be followed until resolution, stabilization, or until it has been determined that the study treatment or participation is not the cause. Serious adverse events that are still ongoing at the end of the study period must be followed up to determine the final outcome. Any serious adverse event that occurs after the study period and is considered to be possibly related to the study treatment or study participation should be recorded and reported immediately.

8.3 Reporting of Serious Adverse Events and Unanticipated Problems

Investigators and the protocol sponsor must conform to the adverse event reporting timelines, formats and requirements of the various entities to which they are responsible, but at a minimum those events that must be reported are those that are:

- related to study participation,
- unexpected, and
- serious or involve risks to subjects or others (see definitions, section 8.1).

If the report is supplied as a narrative, the minimum necessary information to be provided at the time of the initial report includes:

- Study identifier
- Study Center
- Subject number
- A description of the event
- Date of onset
- Current status
- Whether study treatment was discontinued
- The reason why the event is classified as serious
- Investigator assessment of the association between the event and study treatment

8.3.1 Investigator reporting: notifying the Penn IRB

This section describes the requirements for safety reporting by investigators who are Penn faculty, affiliated with a Penn research site, or otherwise responsible for safety reporting to the Penn IRB. The University of Pennsylvania IRB (Penn IRB) requires expedited reporting of those events related to study participation that are unforeseen and indicate that participants or others are at increased risk of harm. The Penn IRB will not acknowledge safety reports or bulk adverse event submissions that do not meet the criteria outlined below. The Penn IRB requires researchers to submit reports of the following problems within 10 working days from the time the investigator becomes aware of the event:

- Any adverse event (regardless of whether the event is serious or non-serious, on-site or off-site) that occurs any time during or after the research study, which in the opinion of the principal investigator is:

Unexpected (An event is “unexpected” when its specificity and severity are not accurately reflected in the protocol-related documents, such as the IRB-approved research protocol, any applicable investigator brochure, and the current IRB-approved informed consent document and other relevant sources of information, such as product labeling and package inserts.)

AND

CONFIDENTIAL

Related to the research procedures (An event is “related to the research procedures” if in the opinion of the principal investigator or sponsor, the event was more likely than not to be caused by the research procedures.)

Reporting Process

Unanticipated problems posing risks to subjects or others as noted above will be reported to the Penn IRB using the form: “Unanticipated Problems Posing Risks to Subjects or Others Including Reportable Adverse Events” or as a written report of the event (including a description of the event with information regarding its fulfillment of the above criteria, follow-up/resolution and need for revision to consent form and/or other study documentation).

Copies of each report and documentation of IRB notification and receipt will be kept in the Clinical Investigator’s study file.

Other Reportable events:

For clinical drug trials, the following events are also reportable to the Penn IRB:

- Any adverse experience that, even without detailed analysis, represents a serious unexpected adverse event that is rare in the absence of drug exposure (such as agranulocytosis, hepatic necrosis, Stevens-Johnson syndrome).
- Any adverse event that would cause the sponsor to modify the investigators brochure, protocol or informed consent form, or would prompt other action by the IRB to assure protection of human subjects.
- Information that indicates a change to the risks or potential benefits of the research, in terms of severity or frequency. For example:
 - An interim analysis indicates that participants have a lower rate of response to treatment than initially expected.
 - Safety monitoring indicates that a particular side effect is more severe, or more frequent than initially expected.
 - A paper is published from another study that shows that an arm of your research study is of no therapeutic value.
- Change in FDA safety labeling or withdrawal from marketing of a drug, device, or biologic used in a research protocol.
- Breach of confidentiality
- Change to the protocol taken without prior IRB review to eliminate apparent immediate hazard to a research participant.
- Incarceration of a participant when the research was not previously approved under Subpart C and the investigator believes it is in the best interest of the subject to remain on the study.
- Complaint of a participant when the complaint indicates unexpected risks or the complaint cannot be resolved by the research team.
- Protocol violation (meaning an accidental or unintentional deviation from the IRB approved protocol) that in the opinion of the investigator placed one or more participants at increased risk, or affects the rights or welfare of subjects.

